A fundamental observation of economics is that the type and number of products in a marketplace can alter a commodity's demand elasticity as well as the type and degree of interaction among those products. As a result, the ability to achieve the tobacco control goals of reducing the consumption of a particular product may be enhanced or diminished via the economic processes of substitution and complementarity (see Bickel, DeGrandpre, et al., 1995 for a review). Substitution, complementarity, and independence are measured by cross-price elasticity of demand and are represented by elasticity slopes that are positive, negative, or near zero, respectively. Studies to date have almost exclusively examined only pairs of products and in very few cases three concurrent commodities. Relevant to this application, the investigators examined the interaction of three commodities in one of their prior studies (Johnson, et al., 2004). Specifically, smokers had access to conventional cigarettes, reduced-nicotine cigarettes, and nicotine gum. When the price of conventional cigarettes increased, consumption of both reduced-nicotine cigarettes and nicotine gum increased even though their prices were fixed. Thus, reduced-nicotine cigarettes and nicotine gum functioned as substitutes for conventional cigarettes. Indeed, by concurrently using both products, the smoker could reproduce different aspects of the conventional cigarette experience by consuming the reduced-nicotine cigarette (i.e., sensory effects associated with combustible tobacco smoke inhalation) and nicotine gum (i.e., central effects associated with nicotine ingestion). Importantly, reduced-nicotine cigarettes functioned as a better substitute than gum when each was offered as a substitute alone (the use of denicotinized cigarettes increased the most).

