$$Q = Q_{alone} * 10^{I * e^{-\beta C}}$$

In this equation, Q_{alone} represents the maximum consumption of the fixed-price commodity when the primary commodity has a price high enough to drive consumption to zero, β is the sensitivity of fixed-price commodity consumption to the price of the primary commodity, I is an interaction parameter that indicates whether the fixed-price commodity is a substitute (positive I value), complement (negative I value), or independent (I value near zero), and Q and C represent consumption of the fixed-price commodity and cost of the primary commodity, respectively, and are known from data. This equation has three parameters (Q_{alone} , I , and β) that will be estimated from experimental data using nonlinear regression. Analysis will proceed similarly as in Aim 1 with the substitution equation being fit to individual subject data to generate subject-specific estimates of maximum consumption, interaction, and sensitivity. These values will then be further analyzed to satisfy the goals of Aim 2.

Primary Analyses of Interest in Aim 2. Aim 2 involves a number of comparisons between demand characteristics (intensity and elasticity) and substitution (maximum consumption, sensitivity, interaction) across and within both doses and conditions involving three types of commodities (reduced-nicotine cigarettes, conventional cigarettes, and other non-combustible products). Within-dose statistical comparisons are briefly described in **Table 2**. Each of these effects will also be compared in larger mixed-effect models across dose with dose entered as a between-subject variable to determine the degree to which these substitution and demand effects differ by dose.

1. Compare substitution (maximum consumption, sensitivity, and interaction) of conventional cigarettes for reduced-nicotine cigarettes and vice versa in condition **d**. In separate pricing scenarios, this condition will include both conventional and reduced-nicotine cigarettes as a constant-price and modified-price commodity, allowing us to assess the degree to which the two cigarette types substitutes for one another. This analysis will inform regulators the degree to which reduced-nicotine cigarettes will, at each of the doses included here, replace conventional cigarettes in the marketplace as a functionally equivalent commodity (substitutes) or act independently in the marketplace without affecting consumption of the other cigarette (independents).

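### Experiment 2: the sign rule for the cross-price interaction parameter I contradicts the printed equation, so substitutes would be labelled complements and complements substitutes

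*Combined protocol and SAP*

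**What the plan says.** The rule is in the Experiment 2 Data Analyses, under General Substitution Analyses Procedure. The equation is printed as "Q = Q_{alone} * 10^{I * e^{-\beta C" (closing brackets omitted here), that is, Q = Q_alone × 10^(I·e^(−βC)). Its terms are defined as follows:

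- **Q and C:** "Q and C represent consumption of the fixed-price commodity and cost of the primary commodity, respectively, and are known from data".
- **Q_alone:** it "represents the maximum consumption of the fixed-price commodity when the primary commodity has a price high enough to drive consumption to zero".
- **β:** "β is the sensitivity of fixed-price commodity consumption to the price of the primary commodity".
- **I:** it indicates whether the "fixed-price commodity is a substitute (positive I value), complement (negative I value), or independent (I value near zero").

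Q_alone, I and β are all estimated for each subject by nonlinear regression. No sign constraint on β is stated.

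The background in section 2.1 of the Experiment 2 IRB application sets out what the categories mean. Substitution, complementarity and independence are "represented by elasticity slopes that are positive, negative, or near zero, respectively". It illustrates substitution with an earlier study: "When the price of conventional cigarettes increased, consumption of both reduced-nicotine cigarettes and nicotine gum increased even though their prices were fixed".

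**The concern.** In the printed equation the exponent shrinks to zero as the primary product becomes dearer. A positive I therefore inflates consumption of the fixed-price product when the primary product is cheap, and that excess disappears as the price rises. Consumption falls as the other product's price goes up, which is what a complement does, yet the plan calls it a substitute.

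I is one of the three substitution parameters named in Aim 2 primary analyses 1 and 4, and it bears on analysis 5, which compares substitution between conditions c and d. Analysis 1 is intended to tell regulators whether reduced-nicotine cigarettes would take the place of conventional ones. Under the written rule, a reduced-nicotine cigarette that smokers do switch to would be reported as a complement. Contrasts in I between conditions or between doses would also be read in the wrong direction.

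**Working it through.** The plan gives no figure to reproduce here. The check is algebraic, with numerical confirmation.

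**Inputs.** The equation, the definitions of Q, C, Q_alone and β, and the sign rule come from General Substitution Analyses Procedure. The meaning of substitute and complement comes from section 2.1 of the Experiment 2 application.

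**Step 1: sign of β.** Q_alone is defined as the level of Q when the primary product is priced out. The equation tends to Q_alone as C grows only if e^(−βC) → 0, which needs β > 0. With β < 0 the curve moves away from Q_alone. For example, Q_alone = 10, I = 0.5, β = −0.3 gives Q = 31.6 at C = 0 and 457 at C = 4.

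**Step 2: limits.** At C = 0, Q = Q_alone × 10^I. As C becomes large, Q → Q_alone.

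**Step 3: slope.** ln Q = ln Q_alone + ln(10)·I·e^(−βC), so

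- d ln Q / dC = −ln(10)·I·β·e^(−βC)
- cross-price elasticity: d ln Q / d ln C = −ln(10)·I·β·C·e^(−βC)

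For β > 0 and C > 0 the elasticity always has the sign opposite to I.

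**Step 4: numbers.** Assumed for illustration: Q_alone = 10, β = 1. The elasticity at C = 1 is −2.303 × I × 0.368 = −0.847 × I.

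| I | Q at C = 0 | C = 1 | C = 2 | C = 4 | very high C | elasticity at C = 1 | pattern by section 2.1 | label by the plan's rule |
|---|---|---|---|---|---|---|---|---|
| −1 | 1.0 | 4.3 | 7.3 | 9.6 | 10 | +0.85 | substitute | complement |
| 0 | 10 | 10 | 10 | 10 | 10 | 0 | independent | independent |
| +1 | 100 | 23.3 | 13.7 | 10.4 | 10 | −0.85 | complement | substitute |

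Across I = −1, −0.5, 0, 0.5, 1 and β = 0.2, 1, 3, all 12 cells with non-zero I had an elasticity opposite in sign to I.

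**Step 5: fitting.** Data were simulated at six prices (0.12, 0.25, 0.5, 1, 2, 4) with Q_alone = 10, |I| = 1, β = 1 and error SD 0.5, all assumed. There were 100 fits per scenario. Data from a true substitute gave I > 0 in 0% of fits, and data from a true complement gave I > 0 in 100%. The result was the same with β held at or above zero and with β free, and no free fit gave a negative β.

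**Step 6: the definition of Q_alone.** The plan describes Q_alone as a maximum. From Step 2, Q_alone exceeds the C = 0 level only if 10^I < 1, that is, I < 0. With I > 0, which the plan labels a substitute, Q_alone is the minimum. So this definition, in the same paragraph as the sign rule, also implies that substitutes have negative I.

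**The case against.** The algebra is not in dispute. The case on the other side concerns consequence and source.

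- **An analyst might not follow the rule literally.** Section 2.1 defines the categories by slope, the team reports having used an analogous modification before, and a plot of the fitted curve would show its direction. This stands as far as it goes: inverted reporting is a risk and has not been shown to occur, and the analysis code is not available to us. But this is the only rule the plan gives for reading I.
- **Much of Aim 2 is untouched.** Estimates, tests of difference and p-values do not depend on the label. Analyses 2 and 3 use demand intensity and elasticity and do not involve I. Conclusions about Q_alone and β are not reversed. Analysis 1 explicitly names only substitutes and independents. All of this is right, and it limits the damage to how I is classified and which way its effects are read.
- **β is a free parameter.** A fit with negative β, possible with only about six noisy prices per subject, would reverse the relation between I and slope. The simulation used fairly clean data and does not exclude such fits. This does not rescue the rule, because negative β contradicts the definition of Q_alone. It is a reason to constrain β.
- **The slip may be in the equation.** A missing minus sign before I would explain the mismatch equally well. The documents cannot settle which element is wrong, but the two cannot both stand.

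**Conclusion.** The concern holds. The equation and the sign rule contradict each other, and the plan's own definitions of substitution and of Q_alone side with a negative I for substitutes in the equation as printed. If the written rule is applied, every non-zero I is misclassified, and the direction of any effect on I in Aim 2 analyses 1, 4 and 5 is inverted. I near zero is labelled correctly either way.

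This rests on β > 0, which the definition of Q_alone requires, and on the printed rule being used as written. It does not affect design, sample size, data collection or model fitting. It should nevertheless be corrected before results are interpreted, because the substitute or complement label is part of what Aim 2 offers regulators.

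**What to change.** Do one of the following, not both:

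- keep the equation and change the text so that negative I means substitute, positive I means complement and I near zero means independent; or
- keep the text and put a minus sign before I, giving Q = Q_alone × 10^(−I·e^(−βC)).

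With either choice:

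- State that β is constrained to be positive, so that the sign of I has one meaning for every subject.
- Define Q_alone as consumption of the fixed-price product at a prohibitive price of the primary product. Drop the description as a maximum, which fails for complements.
- Check that the analysis script, table labels and figure captions follow the chosen convention. A simple test is to confirm that a curve labelled as a substitute rises with C.

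The cost is a few words in the analysis plan and a check of the script. No new data are needed. Any fits already run without the constraint should be screened for negative β and refitted where it occurs.

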cigarettes, usual brand of cigarettes, and other nicotine products will all be available, mimicking a regulatory environment where reduced-nicotine cigarettes are made available in the marketplace, but conventional cigarettes remain available as well. This condition will include double the pricing scenarios such that both reduced-nicotine and conventional cigarettes will alternately serve as the modified-price and constant-price commodity, allowing us to measure symmetrical cross price elasticity for conventional and reduced-nicotine cigarettes (**Table 2**). Participants will be compensated \$20 for the consent session, \$40 for the assessment session, \$20 for each of the four Experimental Tobacco Marketplace sessions, \$20 in experimental income to be kept and/or used for tobacco/nicotine products in the Experimental Tobacco Marketplace sessions, and \$75 for completing all sessions for a maximum total of \$295.

Sample Size Justification

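### Aim 2, primary analysis 1: as worded, comparing the two directions of substitution does not classify the cigarettes as substitutes or independents, and I has no test, interval or limit attached

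*Combined protocol and SAP*

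**What the plan says.** In Experiment 2, Data Analyses, under Primary Analyses of Interest in Aim 2, item 1 is to "Compare substitution (maximum consumption, sensitivity, and interaction) of conventional cigarettes for reduced-nicotine cigarettes and vice versa in condition" d, the marketplace in which both cigarette types are on sale. Each type takes a turn as the constant-price product while the other's price is varied. The Experiment 2 Procedure describes this doubling of price scenarios as "allowing us to measure symmetrical cross price elasticity for conventional and reduced-nicotine cigarettes". Item 1 gives its purpose as "allowing us to assess the degree to which the two cigarette types substitutes for one another". Regulators are then to learn how far reduced-nicotine cigarettes will, at each dose, "replace conventional cigarettes in the marketplace as a functionally equivalent commodity (substitutes) or act independently in the marketplace".

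The general substitution procedure just before it fits Q = Q_alone × 10^(I·e^(−βC)) to each participant's data, to "generate subject-specific estimates of maximum consumption, interaction, and sensitivity". It states that "I is an interaction parameter that indicates whether the fixed-price commodity is a substitute (positive I value), complement (negative I value), or independent (I value"; for that third class the value is to be near zero. What follows the fitting is described only as "These values will then be further analyzed to satisfy the goals of Aim 2". Within-dose comparisons are referred to Table 2, which is not in the supplied text. Across dose, mixed models ask whether the effects differ between dose groups.

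**The concern.** Substitute or independent is an absolute question about each direction: does raising the price of one cigarette change purchases of the other? The comparison item 1 names is relative. Read as a contrast of one direction with the other, its null hypothesis is that the parameters are equal. That null is true for two independents and also for two equally strong substitutes, which are two of the outcomes item 1 has to separate.

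No other listed analysis supplies the missing step. Items 2 and 3 compare own-price demand. Items 4 and 5 concern substitution by other nicotine products. The across-dose models are also relative comparisons.

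At stake is the first listed primary analysis of Aim 2 and a statement addressed to regulators. A non-significant direction contrast could be reported as independence, or as functional equivalence, with nothing in item 1 to choose between them. A significant one could be reported as evidence about replacement in both directions when it shows only that the directions differ.

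**Working it through.** **The plan's own figure.** The Sample Size Justification for Aim 2 gives 30 per dose for a within-factors ANOVA with 4 conditions, f = 0.25, alpha 0.05 and 90% power. Assuming correlation 0.5 and sphericity (neither is stated), λ = f²·n·m/(1−ρ) = 0.0625 × 30 × 4 / 0.5 = 15 on 3 and 87 degrees of freedom. Power is 0.904; at n = 29 it is 0.892. So 30 reproduces. That calculation concerns four conditions. For a two-level contrast at the same f, λ = 0.0625 × 30 × 2 / 0.5 = 7.5 on 1 and 29 degrees of freedom, and power is 0.75.

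**What the direction contrast can show.** The documents give no SD or expected value for I, so effects are in SD units, with positive meaning substitution. Assumptions: n = 30 pairs, unit SDs, two-sided alpha 0.05, correlation 0.5 between directions, 40,000 simulated trials per row.

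| True effect, direction 1 / direction 2 | Direction contrast rejects | Direction 1 vs zero | Direction 2 vs zero |
|---|---|---|---|
| 0 / 0 | 5.0% | 5.1% | 5.0% |
| 0.8 / 0.8 | 5.1% | 98.8% | 98.8% |
| −0.8 / −0.8 | 5.0% | 98.9% | 98.7% |
| 0.8 / 0 | 98.9% | 98.8% | 5.0% |
| 0.8 / 0.3 | 75.0% | 98.8% | 35.7% |

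The first three rows are mutual independents, substitutes and complements, and the direction contrast does not distinguish them. The same holds at equal effects of 0.5 or 1.0 SD, where it rejects about 5% and a one-direction test rejects about 75% and over 99%. The 75% follows from a noncentrality of 0.5 × √30 = 2.74 on 29 degrees of freedom.

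The contrast depends only on the difference. Effects of 0.8 and 0.3 SD (both substitutes) and effects of 0.5 and 0 SD (one independent) both differ by 0.5 SD, and both are rejected about 75% of the time at correlation 0.5 and about 46% at correlation 0. Rejection therefore does not say which class either direction is in.

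**Whether I can do the classifying as printed.** Put Q_alone = 10 and β = 1 into the equation:

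- I = +1: Q is 100 at C = 0, 23.3 at C = 1 and 10 at C = 20.
- I = −1: Q is 1, 4.29 and 10 at the same prices.
- I = 0: Q is 10 throughout.

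Positive I makes purchases of the constant-price product fall as the other's price rises, which is complementarity. The printed rule calls positive I a substitute. It also defines Q_alone as the maximum, which fits only negative I. The sign rule and the equation have to be reconciled before I is used to classify.

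**What an interval can deliver.** With n = 30, the 95% interval half-width is 2.045 × SD / √30 = 0.37 SD. A near-zero limit tighter than 0.37 SD could rarely be met by a 95% interval, even with an estimate of exactly zero. The limit must be chosen with that in mind.

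**The case against.** Four points on the other side carry weight.

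- **Table 2.** The plan sends the within-dose comparisons there, and it is not in the supplied text. It may name a test against zero. Nothing can be held against the plan on what that table contains.
- **The wording.** Item 1 can be read as estimating substitution in both directions; the purpose sentence leans that way, and no equality null is written. That reading stands. It leaves item 1 with no inferential rule at all, so the same wording is needed.
- **The classification exists in words.** I is estimated per participant with a stated reading, and Section 2.1 of the Experiment 2 application describes positive, negative and near-zero cross-price slopes. The information will be collected; only the rule for acting on it is missing.
- **Unequal effects.** A reader might infer that item 1 has no power for its question whatever the truth. The documents do not support that. If both effects are zero they are equal, so rejecting equality of I excludes mutual independence. At 0.5 SD against 0 the contrast rejects about 46% (correlation 0) to 75% (correlation 0.5), and at 0.8 SD against 0 about 85% to 99%. The 5% figure applies only to equal effects, and Section 2.1 of the Experiment 1 application reports a preference for nicotinized cigarettes when both types were available.

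A reader might also infer that fitted I is too error-prone to test. That is not established. Small simulations at assumed prices gave false rejection rates from about 3% to 33%, depending on the optimiser's starting value.

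**Conclusion.** The point holds for the wording of item 1. The only comparison it names does not classify. With equal effects, mutual substitutes and mutual independents give the same 5% rejection rate; with unequal effects, asymmetry is shown and neither direction is classified. The verbal reading of I has no test, interval or near-zero limit in the supplied text, and its sign rule runs against the printed equation.

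A reader might go further and infer that Aim 2 cannot separate substitutes from independents. It can: both directions are observed in condition d, and at 30 per dose a one-direction test against zero has power of about 36% at 0.3 SD, 75% at 0.5 SD and 99% at 0.8 SD. These rates rest on assumed unit SDs and normal values, because the documents give no distribution for I.

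**What to change.** Reword item 1 so that, within each dose and for each direction, the primary result is the cross-price effect with its confidence interval against zero. State in advance a limit for near zero, and conclude independence only when the interval lies inside it, so that non-significance alone is never read as independence.

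For the measure, there are two options:

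- The within-person change in purchases of the constant-price cigarette across the other cigarette's prices, in a form that is defined at zero purchases. A plain log change is not: if purchases were Poisson with mean 1 (the I = −1 case above at C = 0), e^(−1) = 37% of participants would buy none.
- I itself, once its sign rule has been reconciled with the printed equation.

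Keep the direction-against-direction comparison as a secondary analysis, described as a test of asymmetry only. If Table 2 already specifies a test against zero, item 1 should say so.

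The cost is a paragraph of analysis text and no new data. The downside is two tests per dose in place of one, so ten across the five doses rather than five for a given measure.
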